15.5 Interim Analysis

There will be interim reviews conducted by the DMC for the purpose of monitoring study conduct and assessing patient safety at 1/3 and 2/3 goal enrollment. Blinding will be maintained. An O'Brien-Fleming alpha spending function with symmetric stopping boundaries for benefit and harm will be utilized. If the stopping boundaries have been reached (absolute value of z-value >3), the data will be unblinded for review and the trial will be terminated. Finally, there also will be consideration of terminating trial if there is consensus of futility.

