14.1 DMC Charter

Introduction

The purpose of this charter is to define the responsibilities of the DMC, detail membership requirements, describe the data to be reviewed, delineate the meeting process, and outline the considerations and policies of the DMC. The DMC will act in an expert, independent advisory capacity to monitor participant safety, and evaluate the efficacy and conduct of the study.

Study Overview

- Study title: Minimally Invasive Thoracic Surgery Intercostal Nerve Block Trial
- Study design: Randomized, double-blind, active-comparator controlled clinical trial to assess the analgesic efficacy of intercostal nerve block by Liposomal Bupivacaine versus Standard Bupivacaine in subjects undergoing minimally invasive lung resection.
- Phase: III
- Number of participants: 80
- Number of sites: 1

DMC Responsibilities

- Review the research protocol, informed consent documents, and plans for data safety and monitoring prior to initiation of study, periodically during the study, and at the conclusion of the study;
- Conduct interim and final evaluation of the study, including safety data, quality and timeliness of data submission, participant recruitment, accrual and retention, risk versus benefit, including unanticipated problems and protocol violations, efficacy, statistical outcomes, and other factors that can affect study outcome, including aggregate and individual participant data related to safety, data integrity and overall conduct of the study;
- Protect the safety of the study participants;
- Review and evaluate ad hoc safety issues concerning the study at the request of the Investigator;
- Make recommendations to the Investigators concerning continuation, termination, or other modifications of the study based on the observed beneficial or adverse effects of the study;
- Operate according to the procedures described in this charter.

DMC Membership

The DMC will be comprised of an External Investigator, Clinical Pharmacist, and the Medical Monitor who will also serve as the Chairman of the DMC.

- External Investigator: [name], Assistant Professor of Surgery at UCSF. [name] is the Surgical Director of the Enhanced Recovery After Surgery Program in Colorectal Surgery and has expertise in postoperative analgesia.

- Clinical Pharmacist: [name] at UCSF. [name] has expertise pertaining to the efficacy and risks associated with local amide analgesia.

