The DMC reviews data related to study conduct. Data to be reviewed and listed in the DMC reports regarding study conduct includes: summary of protocol violations, completeness and timeliness of study visit data, enrollment eligibility and ineligibility information, noncompliance, unanticipated problems, information concerning withdrawal of participants. The DMC may issue recommendations regarding study conduct when concerns arise that aspects of study conduct may threaten participant safety or study integrity.

DMC Meetings

- Projected Schedule of Meetings

An initial meeting of the DMC will be held prior to any participant enrollment in order for the members to review the charter, form an understanding of the protocol and definitions being used, establish a distribution and meeting schedule, review the study modification and/or termination guidelines, and finalize format and protocol-specified statistical

methods to be used in reports to be considered by the DSMB. Subsequent DMC meetings will be held to review at 1/3 and 2/3 goal enrollment, and at the conclusion of the study.

- Ad Hoc Meetings

An ad hoc meeting of the DMC may be called at any time if imminent participant safety issues arise. If a significant safety concern arises during the study, the DMC Chair may convene a meeting to review safety and any other aspect of the study. Significant safety events may include, but are not limited to, the following:

- A death or life-threatening condition sustained by a participant, regardless of causality
- An unexpected serious safety issue newly identified during the development program that could expose participants to unnecessary risks
- Any other concern regarding participant safety raised by any DMC member

- Meeting Format

DMC meetings will be conducted in person.

- Voting

DMC recommendations will be agreed upon by formal majority vote. In event of a split vote, the DMC Chair will cast the deciding vote.

- Stopping Rules

The DMC will determine whether the study should continue as planned, proceed with modifications, or be terminated. The justification to terminate the study may be due to the DMC's analysis that there is overwhelming effectiveness, futility, or safety issues. If the DMC votes to terminate the study, a final study report will be made.

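### Section 15.5 names an O'Brien-Fleming spending function but gives a single boundary, |z| > 3, that fits neither planned look, and it leaves the endpoint and the effect of crossing unsettled

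*Combined protocol and SAP*

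**What the plan says.** Section 15.5 describes the interim reviews as "for the purpose of monitoring study conduct and assessing patient safety at 1/3 and 2/3 goal enrollment". It then says that an O'Brien-Fleming "alpha spending function with symmetric stopping boundaries for benefit and harm will be utilized". The only number follows: "If the stopping boundaries have been reached (absolute value of z-value >3"), and when that happens "the data will be unblinded for review and the trial will be terminated". The value 3 is not assigned to a look, and neither the test behind z nor the final critical value is given.

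Other sections bear on the same rule:

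- The Synopsis calls the looks safety analyses. Section 14 has the DMC review both safety and efficacy, and the charter (Section 14.1, Review of Other Data) lets it consider early termination for effectiveness or futility.
- Section 15.3 sets a two-sided alpha of 0.05 for the primary endpoint and mentions no adjustment for the looks.
- On authority, the charter says "The DMC will act in an expert, independent advisory capacity to monitor participant safety", "The DMC will determine whether the study should continue as planned, proceed with modifications, or be terminated" and "DMC recommendations will be agreed upon by formal majority vote".
- On timing, it says "An initial meeting of the DMC will be held prior to any participant enrollment". Reviewing the termination guidelines is on that meeting's agenda.

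**The concern.** An O'Brien-Fleming rule has a boundary that falls steeply as information accrues, so one number cannot serve two looks. A constant |z| > 3 is a Haybittle-Peto type rule. A DMC that follows the named method and one that follows the printed number can reach opposite decisions on the same data. At 1/3 enrolment (80/3, about 13 per arm), z = 3.2 crosses 3 but no O'Brien-Fleming boundary. At 2/3, z = 2.7 crosses every O'Brien-Fleming boundary but not 3. Because the boundaries are symmetric, the threshold for harm is just as unclear as the one for benefit.

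Two further gaps make this worse. Without a named endpoint, the DMC does not know what to standardise. And Section 15.5 treats a crossing as ending the trial, while the charter treats termination as one of three options put to a vote.

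**Working it through.** **Inputs.** Looks at information 1/3, 2/3 and 1 (Section 15.5 plus the final analysis). Two-sided alpha 0.05 (Section 15.3; Section 15.5 states none). Mean 35 mg, SD 12 mg, 19% reduction, 80 subjects, 1:1 (Section 15.6). Applying the calculation to the primary endpoint is an assumption, because the documents do not say so.

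**Step 1: try to reproduce 3.** Three usual forms were solved by recursive numerical integration:

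- Spending, half of alpha per side: α(t) = 4[1 − Φ(z₀.₀₁₂₅/√t)]. This spends 0.00021 by t = 1/3 and 0.0121 by t = 2/3.
- Classical: boundary c/√t with c = 2.004, so 2.004/√(1/3) = 3.47 and 2.004/√(2/3) = 2.45.
- Spending on total alpha: α(t) = 2[1 − Φ(1.96/√t)]. This spends 0.00069 by t = 1/3 and 0.0164 by t = 2/3.

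| Rule | Look 1 | Look 2 | Final | Final p |
|---|---|---|---|---|
| Spending, halves | 3.710 | 2.511 | 1.993 | 0.0463 |
| Classical | 3.471 | 2.454 | 2.004 | 0.0451 |
| Spending, total alpha | 3.395 | 2.407 | 2.015 | 0.0439 |
| \|z\| > 3 at both looks | 3 | 3 | 1.975 | 0.0483 |

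The value 3 is not reproduced. Its nominal p is 0.0027, against about 0.0002 to 0.0007 for O'Brien-Fleming at look 1 and 0.012 to 0.016 at look 2. It is too lenient early and too strict later. Whole-patient looks (26 and 53, or 27 and 54, of 80) move the two spending forms only to 3.37–3.76 and 2.39–2.52. A first look would need about 45% to 49% information to give 3; in the classical form, (2.004/3)² = 0.446. Only an unstated total alpha of 0.10 brings the classical look-1 value near 3 (2.96), and look 2 is then 2.09.

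**Step 2: type I error if the final test stays at 1.96.**

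- |z| > 3 at both looks: 0.0027 + 0.0022 + 0.0468 = 0.0517.
- O'Brien-Fleming looks, in table order: 0.0535, 0.0546 and 0.0556.

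**Step 3: how often the stopping decisions differ.** Planned difference 0.19 × 35 = 6.65 mg; d = 6.65/12 = 0.554; drift = 0.554 × √20 = 2.478. A disagreement is a different decision at look 1 or, when both rules continue, at look 2.

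| \|z\| > 3 against | Planned effect: look 1 + look 2 | Null: look 1 + look 2 |
|---|---|---|
| Spending, halves | 0.0470 + 0.1382 = 18.5% | 0.0025 + 0.0087 = 1.1% |
| Classical | 0.0376 + 0.1579 = 19.6% | 0.0022 + 0.0107 = 1.3% |
| Spending, total alpha | 0.0335 + 0.1748 = 20.8% | 0.0020 + 0.0127 = 1.5% |

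If 3 is meant for look 1 only, the planned-effect figure is 3.4 to 4.7%; if for look 2 only, 14.7 to 18.3%. The chance of stopping by look 2 at the planned effect is about 31% under spending (halves) and 18% under |z| > 3.

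**Step 4: how often the final conclusion differs.** With each rule completed by its own final value (6 million simulated trials), significance differs in 1.1 to 2.1% of trials at the planned effect and 0.6 to 1.0% under the null.

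**Step 5: power with 40 per arm.** Fixed design: Φ(2.478 − 1.960) = 69.8%. Spending (halves): 69.2%. |z| > 3 with final 1.975: 69.5%.

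**The case against.** The strongest reply is that little is at stake. Error inflation is slight, final conclusions rarely differ, and the percentages apply only if the looks test the primary endpoint, when the Synopsis and Section 15.5 describe them as safety and conduct reviews. All of that is true and limits the weight of the point. A purely safety reading, however, does not fit boundaries for benefit or the charter's provision for stopping on effectiveness.

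The 18.5 to 20.8% also includes trials that both rules stop, but at different looks. Counting only trials that one rule has stopped by look 2 and the other has not gives 14.4 to 17.9%. This refines the figure without removing the disagreement.

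Section 15.3's 0.05 can be read as the overall level, with an adjusted final value implied by alpha spending. That is a fair reading, but no final value is given anywhere.

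The worked example is on the z scale that Section 15.5 uses. A Student's t of 3.2 on 24 degrees of freedom corresponds to z = 2.89 and would not cross 3, which is one more reason to define the statistic.

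Later steps could settle the matter. But Section 15 requires the separate SAP only before the final analysis, possibly after both looks. The pre-enrolment DMC meeting finalises methods that the protocol specifies, and it is that specification that is inconsistent.

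Finally, a crossing could be read as triggering DMC review rather than ending the trial. The reference to unblinding for review gives that some support, but the statement that the trial will be terminated is firmer than the charter allows.

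**Conclusion.** The concern holds and should be fixed. At two-sided 0.05, |z| > 3 is not an O'Brien-Fleming boundary at either planned look under any of the three usual forms. The endpoint and the final critical value are missing, and automatic termination conflicts with the charter's advisory role and vote. The boundary mismatch rests only on the stated look times and alpha. The disagreement, error and power figures also assume that the looks test the primary endpoint on the z scale; the disagreement and power figures at the planned effect further use the Section 15.6 inputs. On those assumptions the ambiguity mainly changes when the trial would stop, and seldom what it concludes.

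**What to change.** Make the change at or before the pre-enrolment DMC meeting, and in any case before the first look, since a boundary chosen after interim data are seen loses its credibility.

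1. In Section 15.5, name the endpoint and the test statistic to which the boundary applies.
2. If it is the primary endpoint, adopt one consistent rule. Either is acceptable:
   - (a) O'Brien-Fleming spending: |z| ≥ 3.71 at 1/3, ≥ 2.51 at 2/3, and final |z| ≥ 1.993 (p < 0.046).
   - (b) |z| > 3 at both looks, labelled Haybittle-Peto, with final |z| ≥ 1.975 (p < 0.048).

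   Put the matching final level in Section 15.3.
3. If it is a safety endpoint, say so, and state that the primary endpoint is not tested at the looks.
4. Reconcile the termination wording and the stated purpose of the looks across Section 15.5, Section 14, the charter and the Synopsis. Whether a crossing binds or informs the vote is for the sponsor and the DMC to decide.

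The cost is wording in those places and no added subjects. Against the fixed design, power falls by 69.8 − 69.2 = 0.6 points under (a) or 69.8 − 69.5 = 0.3 points under (b). That these figures are below the 80% stated in Section 15.6 is a separate matter, which the choice of boundary neither causes nor cures.

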15.6 Sample Size and Randomization

80 Subjects will be randomized to 1:1 to Liposomal Bupivacaine or Standard Bupivacaine by varying block size (4-8). 80 subjects will provide 80% power to detect a statistically significant effect with 2-sided alpha error set at 0.05 if the measured effect is 19% absolute reduction in cumulative daily in-hospital use of opioids.

The mean daily in-hospital usage of opioids is 35mg morphine equivalents with standard deviation of 12mg. This was estimated by review of previously published studies and corroboration with UCSF clinical practice patterns [12]. A 19% absolute reduction in cumulative daily in-hospital use of opioids corresponds to 1 fewer oxycodone dose per day, which was considered the minimum clinically significant effect.

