| PLANNED INTERIM ANALYSES | When the study has reached 1/3 and 2/3 goal enrollment, interim analysis for safety will be conducted by an independent data monitoring committee. Serious and severe adverse events will be monitored by the committee on an ongoing basis throughout the study. |
| STATISTICS Primary Analysis Plan & Rationale | 
Null Hypothesis: There is no difference in cumulative daily in-hospital use of opioids in subjects who receive intercostal nerve block and wound infiltration with Liposomal Bupivacaine or Standard Bupivacaine during minimally invasive lung resection.
 
Statistical Method: Student's t-test.
 
Rationale: 80 subjects will provide 80% power to detect a statistically significant effect with 2-sided alpha error set at 0.05 if the measured effect is 19% absolute reduction in cumulative daily in-hospital use of opioids.
 |

| | |
|--|---|
| | 
The mean cumulative daily in-hospital usage of opioids is 35mg morphine equivalents with standard deviation of 12mg. This was estimated by review of previously published studies and corroboration with UCSF clinical practice patterns. A 19% reduction in cumulative daily in-hospital use of opioids corresponds to 1 fewer oxycodone dose per day, which was considered clinically significant.
 |
|--|---|

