7.1 Allowed Medications and Treatments

Standardized Hospital Pain Medication Regimen:

Medication will not be given if there is known allergy. Goal pain management is to allow the subject to ambulate and perform incentive spirometry per standard of care. Escalation of opioid dosing if needed will be at the discretion of the inpatient surgery team.

- PO Tylenol 1000mg every 6 hours
- PO Gabapentin 300mg twice a day
- IV Ketorolac 15mg every 6 hours for 24 hours, then PO Diclofenac 50mg BID (if <75 years old and normal renal function)
- PO Oxycodone 5-10mg every 4 hours as needed for moderate pain
- IV Hydromorphone 0.2-0.4mg every 2 hours as needed for severe pain

Standardized Discharge Pain Medication Regimen:

All subjects to be discharged on the following pain regimen outlined below. Medication will not be given if there is known allergy.

- PO Acetaminophen 1000mg every 6 hours for 2 weeks
- PO Gabapentin 300mg twice a day for 2 weeks
- PO Diclofenac 50mg BID for 2 weeks
- PO Oxycodone as needed for pain – 20 Pills in Total

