15.3 Analysis of Primary Endpoint

Null Hypothesis: There is no difference in cumulative in-hospital use of opioids in subjects who receive intercostal nerve block and wound infiltration Liposomal Bupivacaine or Standard Bupivacaine during minimally invasive lung resection.

Student's t-test will be used to assess the means of the cumulative total of in-hospital oral morphine equivalents. It is presumed that the data will be normally distributed. If this assumption is not met, transformation or nonparametric tests (Mann-Whitney U test) will be used. Moreover, as there are only 40 subjects per group, it is possible that we do not achieve effective randomization. If this occurs, we will utilize linear regression adjusting for age, sex, race, comorbidity, diagnosis, and procedure performed. A power of 0.8 and 2-sided alpha error set at 0.05 will be used to assess for statistical significance.

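### The stated 80% power does not follow from the stated inputs: 35 mg/day, SD 12 mg, a 19% reduction and 40 per arm give about 69%

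*Combined protocol and SAP*

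**What the plan says.** Section 15.6 sets the design at 80 subjects, randomised 1:1, and claims that "80 subjects will provide 80% power to detect a statistically significant effect with 2-sided alpha error set at 0.05". The effect to which this claim refers is a 19% fall in daily opioid consumption, labelled absolute. The inputs follow: "The mean daily in-hospital usage of opioids is 35mg morphine equivalents with standard deviation of 12mg". The effect is tied to a clinical anchor: "A 19% absolute reduction in cumulative daily in-hospital use of opioids corresponds to 1 fewer oxycodone dose per day", which the section treats as the smallest effect of clinical importance. The Synopsis (Statistics) repeats the power claim, the mean, the SD and the anchor, though its version of the anchor omits the word absolute: "A 19% reduction in cumulative daily in-hospital use of opioids corresponds to 1 fewer oxycodone dose per day".

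Section 15.3 names Student's t-test, presumes normality (transformation or Mann-Whitney only if that fails) and gives 40 subjects per group. It says the test will "assess the means of the cumulative total of in-hospital oral morphine equivalents", and its null hypothesis does not contain the word daily, whereas the one in the Synopsis does. Section 7.1 lists "PO Oxycodone 5-10mg every 4 hours as needed for moderate pain". The documents give no factor for converting oxycodone to oral morphine equivalents.

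**The concern.** Everything needed to recompute the power is printed, and the result falls about 11 percentage points short of the claim. This paragraph is the only justification for the sample size, and it errs in the favourable direction.

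What is at stake is mainly how a null result would be read. Section 2 says that the drug would only add to health-care costs if it is not found efficacious, and Sections 14.1 and 15.5 let the DMC consider stopping for futility. Anyone who believes the trial had 80% power for the smallest worthwhile effect will give a negative or unpromising result more weight than the design supports.

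Two related gaps limit what a corrected figure can mean. The size of the effect in mg cannot be verified, because one oxycodone dose covers a range and no conversion is stated. And the inputs describe use per day, whereas Section 15.3 tests the total over the stay.

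**Working it through.** **Inputs.** Mean 35 mg/day, SD 12 mg, 19% reduction, 1:1 allocation, two-sided alpha 0.05 (Section 15.6 and Synopsis); 40 per group, Student's t-test, normal data (Section 15.3). I take 35 mg as the control mean and 12 mg as the common SD, which is how a single mean and SD are read for this test.

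**Attempt to reproduce 80%.**
- Difference: 0.19 × 35 = 6.65 mg. Standardised difference: d = 6.65 / 12 = 0.554.
- Noncentrality: d × √(40/2) = 0.554 × 4.472 = 2.478, with 78 degrees of freedom and critical value 1.991.
- Power from the noncentral t distribution: **68.7%** (normal approximation 69.8%). Type II error: 31.3%.

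**What 40 per arm does support.** 80% power needs d = 0.634, so 0.634 × 12 = 7.61 mg, and 7.61 / 35 = 21.7%. Alternatively, with 6.65 mg the SD would have to be 6.65 / 0.634 = 10.5 mg. For reference, 80% power at 6.65 mg and SD 12 mg needs 52.1, rounded up to 53 per arm (106 in total).

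**Rounding of the printed inputs (common SD).**

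| Reduction | Mean (mg) | SD (mg) | Power |
|---|---|---|---|
| 18.5% | 35 | 12 | 66.4% |
| 19.5% | 35 | 12 | 71.0% |
| 18.5% | 34.5 | 12.5 | 61.6% |
| 19.5% | 35.5 | 11.5 | 75.8% |

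Even with all three inputs rounded in the favourable direction, the result stays below 80%.

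**Calculations other than the stated one.**

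| Calculation | Power | Departure from the plan |
|---|---|---|
| One-sided alpha 0.05 | 79.2% | The plan says two-sided |
| Log scale, CV 12/35 in both arms (log SD 0.333, d = 0.211/0.333 = 0.632) | 79.7% | The plan tests untransformed means |
| Difference of 7.5 mg | 78.8% | 21.4% of 35, not 19% |
| SD proportional to the mean (treated SD 9.72) | 76.7% | The plan gives one SD |
| Difference of 19 mg (absolute taken literally) | above 99.9% | Does not give 80% either |

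**The clinical anchor.** At 40 per arm and SD 12 mg, power is 45% for a 5 mg difference, 79% for 7.5 mg and 96% for 10 mg of morphine equivalents. So the unstated conversion matters: 6.65 mg equals 5 mg of oxycodone only at a ratio of 6.65 / 5 = 1.33, and 7.5 mg would imply 1.5. Neither ratio is in the documents.

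**Daily use or total.** A total over the stay also varies with length of stay. As an illustration only, on assumptions not in the documents, let the total be daily use times stay, the two independent, and the 19% reduction apply to the total. The CV of the total is √[(1 + (12/35)²)(1 + c²) − 1], where c is the CV of stay. For c = 0, 0.25 and 0.50 this gives 0.34, 0.43 and 0.63, and power of 69%, 49% and 27%. The 69% figure therefore applies only to a daily-use endpoint.

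**The case against.** The arithmetic is not in dispute; the objections concern how firmly the claim can be called wrong.

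The plan does not say which arm the mean and SD describe, nor that the SD is equal in both. If the SD shrinks with the mean, power is 76.7%. With a 19.5% reduction it becomes 79.0%, and with all three inputs rounded favourably 83.4%. With a common SD, if 35 had been rounded to the nearest 5 and the true value were 37.5 mg, the most favourable rounding gives 80.2%. And because the cited source studied liposomal bupivacaine, 35 mg might be the mean in that arm. The control mean would then be 35 / 0.81 = 43.2 mg, the difference 8.2 mg and power about 86%.

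These readings are possible, but each needs something the plan does not state. One SD given alongside Student's t-test means a common SD, and a mean quoted as the base for a reduction is naturally the comparator's. The 75.8% ceiling holds on those terms, with each figure rounded to its last printed digit. What stands is that the sponsor may have used a different calculation, so it should be asked before any figure is replaced.

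A second objection is that the error leaves type I error, estimation and safety untouched, that a null result is judged mainly by its confidence interval, and that the daily-versus-total question is a separate matter. The first two parts are fair, but they do not make a wrong power statement acceptable as the sole justification for the sample size. The endpoint mismatch is not needed to show the error; it matters here because a corrected sentence has to name the endpoint it describes.

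**Conclusion.** The concern holds. On the plan's own inputs, power is about 69% rather than 80%, and the type II error about 31% rather than 20%. With 40 per arm, the difference detectable with 80% power is 7.6 mg/day (about 22%), not 6.65 mg (19%). This rests on 35 mg being the control mean, a common SD of 12 mg, normal data, 40 analysed per arm and a daily-use endpoint. It makes no allowance for the O'Brien-Fleming interim looks in Section 15.5, which would lower power slightly further. The documents do not show where 80% came from. This needs correcting before the plan is relied on, although it does not require a larger trial. As a minor point, 19% of a mean is a relative reduction, not an absolute one.

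**What to change.** Keep 80 subjects. The sponsor should state how 80% was obtained: per-arm means and SDs, the effect in mg, sidedness, scale and software. Unless it documents a different calculation and corrects the inputs to match, Section 15.6 and the Synopsis should read along these lines:

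> 80 subjects (40 per arm) give about 69% power for a 6.65 mg/day (19% relative) reduction and 80% power for a 7.6 mg/day (about 22%) reduction, SD 12 mg, two-sided alpha 0.05.

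In addition:
- delete the word absolute in Section 15.6 and in the Synopsis;
- give the effect in mg of oral morphine equivalents, with the conversion factor and the dose meant by one oxycodone dose;
- say that the figures apply to daily use, and reconcile this with Section 15.3, so that the endpoint powered is the endpoint tested.

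The cost is wording in two places and one reconciling sentence. No patients are added and no clinical procedure changes; the stated power becomes less favourable.
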